(1) Raw Weight Loss	Digital scale (to nearest 0.1 pounds) with the participants wearing light clothing, no shoes.
(2) Body Mass Index (BMI)	Digital scale and height (to nearest 0.5 cm, via Accustat Genentech stadiometer)
(3) Excess Weight Loss (EWL)	Pre-MBS weight - follow up weight)/(Pre-MBS weight - ideal body weight) × 100%

2 outcomes. We will use the Generalized Linear Model (GZLM) to model the impact of the intervention developed in AIM 2 for dependent effects.

Much like the General Linear

(4) Body Composition	InBody570 body composition analyzer- muscle, fat and total body water measures
Comorbidity Resolution	
(1) Cardiometabolic Profile	lipids, insulin, glucose, blood pressure

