Model that allows for variation in type and scale characteristics of the independent effects, the GZLM extends this versatility to include various types of dependent variables.⁹⁹ In GZLM, the relationship between the independent variables and the dependent outcomes is specified by way of a link function that defines the functional form of this relationship (e.g., when the dependent variable is a proportion, a logistic link function might be used). Through different specifications of the link and probability functions, one generalized model is used to examine the statistical relationships between the design parameters (i.e., independent variables) and the dependent variables, regardless of their scale properties. Statistical consideration is given to repeated measures (pre-, 3-, 6-month post-MBS data). Since the time component has only 2 levels (e.g., 1 pre, 2 post-MBS), there are minimal statistical complications associated with the autocorrelation structure of repeated measures. Measures taken at baseline will be included in the GZLM as covariates to ensure pretest balance and as a control on regression to the mean. Changes in weight will be analyzed by employing a generalization of the t-test, known as Hetelling's T² test. This approach is very important in this case, since it same approach employed in the design. We shall assume a more conservative type I error of 1% to adjust for multiplicity.¹⁰⁰ Missing Values: GZLM models will efficiently use the longitudinal data and accommodate attrition that is ignorable (essentially, missing at random, MAR).¹⁰¹ To assess sensitivity to MAR we will use approaches for the multivariate normal setting and others if normality is not reasonable.¹⁰¹ This avoids the problem of eliminating subjects with incomplete repeated measurements. SAS and JMP (SAS Institute, Cary, NC) will be the primary statistical software packages. *Quality Control.* PI [name] will coordinate the QA/QC protocol with clinical and research staff. Appropriate checks will be conducted prior to, during, and after the completion of data collection.

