- **Statistical Power for AIM 3.** A single-factor, repeated measures design with a sample of 20 subjects, measured at baseline, 3-, and 6-months, achieves 80% power to detect a contrast using a multivariate T² test at a 0.01 significance level. We reduce the type I to a more conservative 1% to correct for multiplicity. The standard deviation across subjects at the same time point is assumed to be 1. The pattern of the covariance matrix is to have all correlations equal with a correlation of 0.25 between the first and second time point measurements.¹⁰⁰⁻¹⁰³ The value of the contrast applied to the hypothesized means is 1.⁹⁷ However, since we are anticipating an attrition rate of ~10%, we will recruit 22 adolescent MBS patients.

Data and Safety Monitoring

- *Data and Safety Monitoring:* All subjects will have an assigned unique study identification number used on all data forms and instruments. Data are computer-linked to the remainder of the dataset on

each individual, and linking information between personal identifiers and study numbers is kept in a locked file cabinet in the Principal Investigator's Office. Certain program staff (e.g., principal investigator, clinical team of [name], [name], and [name], study coordinator) will have access to confidential information needed to perform their respective duties, but the rest of the research staff are not privy to confidential information.

- *Potential Adverse Events.* None of the proposed procedures involve invasive methods of data collection. Most of the proposed methods are part of, or an extension of, the standard of care to assess pre-post MBS surgery mental and physical health and are minimal risk. These studies present minimal discomforts to the patient. Should any adverse events occur during this protocol, the medical facilities at University of Texas are prepared to care for the study participants. All participants will be debriefed regarding any serious health information that might be discerned in the protocol.
- *Description of Adverse and Serious Adverse Events:* Adverse events and serious adverse events identified for study participants that will be reported during protocol are: Adverse Events
 1. Family Crises
 2. Possible Violation of Confidentiality
 3. Extreme Distress due to Assessment Procedures
 4. Extreme Embarrassment or Distress in
Response to Disclosing Sensitive Personal Information

Serious Adverse Events

1. Suicidal Thoughts or Attempts
2. Abuse

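### Three assessment occasions are counted as two levels of time, leaving the GZLM without a stated within-subject covariance and baseline with two roles

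*Combined protocol and SAP*

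**What the plan says.** The Data Analysis Plan (under Study Measures) names a GZLM for the Table 2 outcomes and describes its link and probability functions. It names no within-subject covariance structure, random effect, GEE or robust standard error.

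It says that repeated measures are taken into account and lists them as the pre-operative, 3-month and 6-month data. The next sentence, on autocorrelation, reads: "Since the time component has only 2 levels (e.g., 1 pre, 2 post-MBS), there are minimal statistical complications". It then adds: "Measures taken at baseline will be included in the GZLM as covariates". Changes in weight are assigned to Hotelling's T² at a 1% type I error. The opening of the same section describes the dependent measures as pre-to-post changes.

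Statistical Power for AIM 3 describes "A single-factor, repeated measures design with a sample of 20 subjects, measured at baseline, 3-, and 6-months", with equal correlations of 0.25. The Measures section gives the same three occasions for the anthropometric and cardiometabolic data.

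**The concern.** The bracket in the sentence on levels adds to three, not two, and the count is the only reason given for setting the autocorrelation structure aside. With two occasions there is one correlation and nothing to choose. With three there are three correlations, and equal, decaying or unrestricted patterns give different SEs for the same contrast.

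Because the question is set aside, nobody following the plan knows what dependence to fit for BMI, body composition, lipids, insulin, glucose or blood pressure. A plain GZLM treats all records as independent unless something is added. The role of baseline is also open: if it is one of the repeated outcomes it should not also be a covariate for itself.

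At stake are the SEs, and so the 1% tests, for those outcomes. The plan's claim that the GZLM accommodates attrition that is missing at random is also affected. Likelihood methods support that claim when the within-subject dependence is modelled; an independence model in general does not. With about 20 subjects, an open choice of structure can also be made after the data are seen.

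**Working it through.** **Inputs.** From Statistical Power for AIM 3: n = 20, three occasions, α = 0.01, stated power 80%, contrast value 1; "The standard deviation across subjects at the same time point is assumed to be 1"; "all correlations equal with a correlation of 0.25 between the first and second time point measurements". Not given: the contrast coefficients, the mean vector and the sidedness.

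**1. Reproduce the plan's figure.** For the joint T² test under equal correlation, λ = n·Σ(μ_t − μ̄)² / [σ²(1 − ρ)]. With assumed means (0, 1, 1), Σ(μ_t − μ̄)² = 2/3, so λ = 20 × 0.6667 / 0.75 = 17.78. On F(2, 18) this gives power of 78.9%. A single pairwise contrast has SD √(2 × 0.75) = 1.225. On 19 df, two-sided, its power is 77.4% at n = 20 and 80.3% at n = 21. Other assumptions give 62.8% (joint test, means 0, 0.5, 1) and 89.7% (contrast −1, 0.5, 0.5). Rescaling the coefficients moves the figure between 25.8% (−2, 1, 1) and 98.3% (unit length). So the stated 80% can be matched, on assumed coefficients, by a calculation with three occasions and a correlation of 0.25.

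**2. Does the pattern matter with three occasions?** The number of correlations is k(k − 1)/2: one for k = 2, three for k = 3. Take the baseline-to-6-month contrast of 1 at n = 20:
- Equal correlation 0.25 (the plan): SD √[2(1 − 0.25)] = 1.225, power 77.4%.
- AR(1) with 0.25 between neighbours (assumption): the baseline-to-6-month correlation is 0.25² = 0.0625, SD √[2(1 − 0.0625)] = 1.369, power 65.7%.

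**3. What would default independence do at ρ = 0.25?** With SD 1 and n = 20:

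| Quantity | Correct SE | SE under independence | Ratio |
|---|---|---|---|
| Change, raw values modelled | √[2(0.75)/20] = 0.274 | √(2/20) = 0.316 | 1.15 |
| Mean of two post visits | √[(1.25/2)/20] = 0.177 | √(0.5/20) = 0.158 | 0.89 |
| Same, baseline-adjusted | √(0.5625/20) = 0.168 | √(0.46875/20) = 0.153 | 0.91 |

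The third row uses the correlation of the post visits given baseline: (ρ − ρ²)/(1 − ρ²) = 0.1875/0.9375 = 0.20. The ratio is then 1/√1.20 = 0.913. The variances in that row are (0.9375 + 0.1875)/2 = 0.5625 and 0.9375/2 = 0.46875.

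**4. Error rates (normal approximation, critical value 2.576).** The true size is 2[1 − Φ(2.576 × ratio)]: about 0.3% for the change, 2.1% for the unadjusted post average and 1.9% for the adjusted one, against a nominal 1%.

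**5. Sensitivity.** Only 0.25 is in the documents; the other two rows are assumptions.

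| ρ | Change, 1/√(1 − ρ) | Post mean, 1/√(1 + ρ) | Adjusted post mean | Size, adjusted |
|---|---|---|---|---|
| 0.25 | 1.15 | 0.89 | 0.91 | 1.9% |
| 0.50 | 1.41 | 0.82 | 0.87 | 2.6% |
| 0.75 | 2.00 | 0.76 | 0.84 | 3.1% |

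**The case against.** The strongest reply is that the plan does not dismiss within-subject correlation. It says that repeated measures are considered, its power calculation carries a correlation of 0.25, and nowhere does it specify an independence model. That stands. A reader might infer that the plan's SEs will be wrong; the documents show only that they are not determined.

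A reader might also infer that every Table 2 result is affected. That is not so. Weight change goes to Hotelling's T², which estimates an unrestricted covariance and does not depend on the remark about levels.

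Next, the two levels may mean the two post-operative visits, with baseline as covariate and change as the response. On that reading the 15% error does not arise, because it needs raw values at all occasions to be modelled as independent. But the bracket counts the pre-operative visit, and two visits from one patient remain correlated. Subtracting baseline from both post values while also adjusting for it only shifts the baseline coefficient by 1 and leaves the residuals unchanged. The 9% figure therefore survives this reading.

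It may also be tempting to argue that baseline cannot be a covariate for weight loss because everyone starts at zero loss. The text refers to measures taken at baseline, most naturally measured weight or BMI, so that argument fails.

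Finally, this is a single-group proof-of-concept study in an early, pre-efficacy phase. That limits the consequences but does not supply the missing specification.

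**Conclusion.** The point holds as an internal contradiction and a gap in specification. Time has three levels, the stated reason for not addressing the correlation structure is therefore wrong, the GZLM has no named within-subject covariance, and baseline has two roles. It concerns the Table 2 outcomes analysed by GZLM, not the T² analysis of weight change.

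The size is conditional on default independence, equal correlation and the plan's ρ of 0.25. The SE of a change from raw values would then be about 15% too large, which is conservative. The SE of a post-visit average would be about 11% too small, or about 9% after baseline adjustment, giving a true size of about 1.9% for a nominal 1% test. Higher correlations would make this worse, but they are not in the documents, so the larger inflations in the sensitivity table should not be read as properties of this plan. The correction is worth making before analysis because it is cheap and removes a choice that could otherwise follow the data.

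**What to change.** - Correct the text to three time points: baseline, 3 months and 6 months.
- For continuous GZLM outcomes, prespecify a repeated-measures model with a stated within-subject covariance, for example unstructured with Kenward-Roger degrees of freedom. Other structures are defensible if named in advance.
- For binary outcomes, prespecify GEE with a small-sample correction. Ordinary GEE needs stronger assumptions about missing data than missing at random, so say how the plan's statement on attrition will be met for these outcomes.
- Give baseline one role: either the first of three outcomes, or a covariate with 3 and 6 months as the outcomes.

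The cost is SAP wording and standard SAS code. With about 20 subjects there are a few more parameters to estimate: an unstructured covariance over three occasions has six (three variances, three covariances), against two for equal variances and equal correlation. With baseline as a covariate and two post-operative outcomes, it has three.

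### Weight change is assigned to Hotelling's T², which as normally run drops anyone with a missing weight, while the missing-data text covers only the GZLM; the plan should name one governing weight analysis that uses all observed weights

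*Combined protocol and SAP*

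**What the plan says.** All of this stands in the Study Measures section, mainly in its Data Analysis Plan.

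- **Test for weight.** "Changes in weight will be analyzed by employing a generalization of the t-test, known as Hetelling's" T². The reason given is "This approach is very important in this case, since it same approach employed in the design". Statistical Power for AIM 3 indeed uses a multivariate T² test: 20 subjects at baseline, 3 and 6 months, 80% power, significance level 0.01. It recruits 22 to allow for about 10% attrition.
- **Model for Table 2.** "We will use the Generalized Linear Model (GZLM) to model the impact of the intervention developed in AIM 2 for dependent effects". Table 2 lists raw weight loss, BMI and excess weight loss, so weight falls under this model too.
- **Missing values.** "GZLM models will efficiently use the longitudinal data and accommodate attrition that is ignorable" (MAR). Then: "To assess sensitivity to MAR we will use approaches for the multivariate normal setting", with other approaches if normality is not reasonable. Then: "This avoids the problem of eliminating subjects with incomplete repeated measurements". Only the first of these sentences names a model, and it is the GZLM.
- **Source of weights.** Measures says that anthropometric data are collected at baseline, 3 and 6 months as part of routine care. Study Procedures adds that BMI before and after surgery is taken from medical records, with record data gathered to 18 months after surgery.

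**The concern.** The standard one-sample T² for three time points works on each participant's pair of changes from baseline, so a participant without the 3- or 6-month weight contributes nothing. That is a property of the standard test; the plan does not state it. The plan gives no imputation, likelihood or other incomplete-data form of T². The analysis that was powered is therefore the one that the missing-data text does not reach, although that text presents keeping incomplete subjects as a benefit of the approach.

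Two things are at stake. If a missing 6-month weight depends on early weight loss, completers differ from the full group and the estimate is biased; Background Information itself calls attrition a significant challenge in these patients. And with two weight analyses and no stated order between them, about 20 participants can yield two different answers, with the choice open once it is known who is missing.

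**Working it through.** **1. Reproduce the stated power.** Inputs from Statistical Power for AIM 3: n = 20, SD 1, all correlations ρ = .25, contrast value 1, α = .01. The mean pattern is not given, so it is assumed below.

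Each change from baseline has variance 2(1 − ρ) = 1.5, and the two changes have covariance 1 − ρ = .75. The determinant is 1.5² − .75² = 1.6875. For mean changes d = (d₃, d₆), power comes from a noncentral F(2, n − 2) with

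λ = n(1.5d₃² + 1.5d₆² − 1.5d₃d₆)/1.6875.

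- d = (1, 1): λ = 20 × 1.5/1.6875 = 17.8, power .789.
- d = (.5, 1): λ = 20 × 1.125/1.6875 = 13.3, power .628.

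The single 6-month-minus-baseline contrast has SD √1.5 = 1.225. Its two-sided noncentral t parameter is √20/1.225 = 3.65, giving power .774 whatever the 3-month mean.

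So the stated 80% is reproduced within about one point for T², but only if the 3-month change is also 1 SD (or zero, which gives the same λ).

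**2. Random attrition.** Expected completers are 22 × .9 = 19.8.

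| Complete | T², d = (1, 1) | 6-month contrast |
|---|---|---|
| 22 | .849 | .828 |
| 20 | .789 | .774 |
| 18 | .713 | .708 |

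Averaged over Binomial(22, .9), T² power is .778 and contrast power .765. Recruiting 22 therefore covers most of the loss.

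**3. Selective attrition under MAR (simulation).** Assumptions: 22 enrolled, ρ = .25, true change −1 SD at 3 and 6 months, baseline and 3-month weights complete, 10% of 6-month weights missing, with a logistic dependence on the 3-month change. The slope is not in the documents, so a strong value (1.5 per SD) and a weak one (.5) are shown.

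| Who leaves | Slope | Completer 6-month change | T² power |
|---|---|---|---|
| Those losing less | 1.5 | −1.08 | .92 |
| Those losing more | 1.5 | −0.93 | .70 |
| Those losing less | .5 | −1.03 | .83 |
| Those losing more | .5 | −0.97 | .74 |

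At slope 1.5 the bias is about .075. The standard error is about 1.225/√20 = .274, and .075/.274 ≈ 0.3. A likelihood estimate from all observed weights is within .004 of −1 in these settings.

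**4. How far this depends on the assumptions.**
- At ρ = .8 and slope 1.5, the bias at 10% missing is about 4%. Power exceeds .999 even with 18 complete, so only bias and type I error remain at issue.
- If dropout depends on the 3-month value rather than the change, the 6-month bias is zero under equal correlations.
- If dropout depends on the unseen 6-month change (not MAR), the likelihood estimate is also biased: about 9%, against 15% for completers, at 10% missing.
- The likelihood-based 6-month contrast has simulated power of .77 to .79 at 10% missing and slope 1.5, much the same as T² under random attrition (.78).

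**The case against.** The strongest reply is that a weight analysis meant to keep incomplete subjects is already planned: the GZLM covers Table 2, takes the pre-surgery, 3- and 6-month data, and is said to accommodate MAR attrition. That stands, and a reader should not infer that every weight analysis in the plan drops incomplete subjects. The gap is that the plan does not say which analysis governs, while its specific sentence on weight and its power statement both point to T².

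Second, approaches for the multivariate normal setting might be read as reaching T². They are offered only to examine sensitivity to MAR, with no method named, so they do not define the main analysis.

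Third, leaving the study need not mean a missing weight, because weights come from routine care and the medical record. This also stands. No visit window is given, so it reduces the problem without removing it.

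Three stronger readings are tempting and not supported:
- *Attrition undermines the planned power.* At random 10% loss it does not (.778).
- *Completers will overstate weight loss.* Nothing says who would leave; the bias can go either way.
- *The 1% error rate fails in a way that matters.* T² type I error does rise to about .016 under the strong selection above, but only if mean weight does not change at either visit, a null of little practical relevance after bariatric surgery.

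**Conclusion.** The point holds as a gap between the powered weight analysis and the missing-data plan, and as a missing statement of which weight analysis governs. It should be corrected, but it is not a fatal flaw.

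At the plan's own attrition of about 10%, strong selection shifts the completer estimate by 7 to 8% (about 0.3 standard errors) in either direction and moves T² power to about .92 or .70. Weak selection shifts it by about 3%, with power .74 to .83. These figures rest on the plan's SD and correlation, an assumed 1 SD change at both visits, an assumed selection slope, and study attrition being equal to missing 6-month weights; the last probably overstates the problem.

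The gain from a likelihood model is less bias under MAR and use of every observed weight. A reader might also expect more power, but for the 6-month contrast there is none to claim.

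**What to change.** State that the governing weight analysis is a likelihood-based repeated-measures model on all observed baseline, 3- and 6-month weights, including those found in the medical record. Specify:

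- time as a three-level factor (the present text reads "Since the time component has only 2 levels (e.g., 1 pre, 2 post-MBS", which counts three occasions as two levels);
- unstructured covariance and a small-sample degrees-of-freedom correction;
- baseline as a response, and not also as a covariate.

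Name one test and restate its power with 20 complete. The 6-month-minus-baseline contrast has about .77 and does not need the unstated 3-month mean. The 2-df joint time test has about .79 if the 3-month mean change is also 1 SD, and .63 if it is .5 SD. Keep T² as a complete-case sensitivity analysis, and apply the planned MAR sensitivity work to the governing model.

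The cost is some analysis-plan wording and one revised power sentence. No visits or participants are added, and the model runs in SAS, which the plan already names. The drawbacks are the degrees-of-freedom correction needed at about 20 participants and a stated power slightly below 80%.
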